3.5.5 C-SSRS Data

The Columbia Suicide Severity Rating Scale (C-SSRS) is an assessment that evaluates suicidal ideation and behavior. There are 5 “Yes/No” questions on suicidal ideation following the increasing severity order: (1) Wish to be dead, (2) Non-specific active suicidal thoughts, (3) Active suicidal ideation with any methods (not plan) without intent to act, (4) Active suicidal ideation with some intent to act, without specific plan, (5) Active suicidal ideation with specific plan and intent, and 6 “Yes/No” questions on suicidal behavior following the increasing severity order: (6) Preparatory acts or behavior, (7) Aborted attempt, (8) Interrupted attempt, (9) Actual attempt, (10) Suicidal behavior, (11) Suicide (only at post-baseline visits). Another “Yes/No” question of whether the subject has engaged in non-suicidal self-injurious behavior is also collected.

The summary table for C-SSRS will be conducted for the placebo-controlled and LTE active treatment period. Number of subjects who answered “Yes” to each of the 11 questions post-baseline, subjects who answered “Yes” to at least one question for suicidal ideation, subjects who answered “Yes” to at least one question for suicidal behavior, and subjects who have engaged in non-suicidal self-injurious behavior will be presented. A listing of subjects with any suicidal ideation or behavior at baseline or post-baseline will be provided for placebo-controlled and LTE period.

3.5.6 ECG Data

Shift from normal or unknown ECG at baseline to abnormal, not adverse event or abnormal, adverse event post-baseline ECG will be summarized for the placebo-controlled and LTE active treatment group. For early start subjects, the placebo-controlled baseline will be used. For late start subjects, the LTE baseline will be used. Subjects with abnormal ECG status will be listed.

3.5.7 Vital Sign Data

Vital sign parameters include body temperature, systolic blood pressure, diastolic blood pressure, heart rate, respiration rate and weight. Vital signs will be measured with the subject

CONFIDENTIAL

The information contained herein may not be used, disclosed, or published without the written consent of Biogen MA Inc.

supine and after the subject has been resting for at least 10 minutes. The descriptive statistics for actual values will be summarized at each visit in the placebo-controlled and LTE period. Plot of mean vital sign values in the placebo-controlled and LTE period will be provided.

Summary of change from baseline including number of evaluable subjects, mean, standard deviation, median, 25% and 75% quartiles, minimum, and maximum values will be summarized at each visit in the placebo-controlled and LTE active treatment period. Placebo-controlled baseline will be used for early start subjects and LTE baseline will be used for late start analysis.

The analysis of vital signs will also focus on the incidence of clinically relevant outliers. Please refer to the placebo-controlled SAP for the criteria to assess potential clinically relevant outliers in vital sign. The incidence and percentage of clinically relevant outliers determined by each criterion will be summarized in the placebo-controlled and LTE active treatment period. A listing of subjects with clinically relevant vital signs in the placebo-controlled and LTE active treatment period will also be provided.

Visit windows for by visit summaries

For vital sign by visit summaries, the analysis visit should be defined using windows (see Table 6 below). For the same parameter for a subject, if there is more than 1 record in the same analysis visit window, then select the record closest to the target visit day. If there are 2 records in the same analysis visit window with the same distance from the target visit day, then select the record with the later date.

Table 6: Visit Windows for Vital Sign by Visit Summaries

Analysis visit	Analysis visit window ¹	
	For subjects who received the first dose of aducanumab in the placebo-controlled period	For subjects who received the first dose of aducanumab in the LTE period
Baseline	Last value prior to the first dose of aducanumab	Last value prior to the first dose of aducanumab
Week 4	[2, 42]	[2, 42]
Week 8	[43, 70]	[43, 70]
Week x	[7x -13, 7x+14] for $8 \leq x \leq 72$	[7x -13, 7x+14] for $8 \leq x \leq 252$
...
Week 76	[519, the end day of the placebo-controlled period ¹]	[7x -13, 7x+14] for $8 \leq x \leq 252$
Week 80	[the start day of the LTE period ² , 574]	[7x -13, 7x+14] for $8 \leq x \leq 252$
Week x	[7x -13, 7x+14] for $84 \leq x \leq 176$	[7x -13, 7x+14] for $8 \leq x \leq 252$
...
Week 180	[1247, 1267]	[7x -13, 7x+14] for $8 \leq x \leq 252$
Week 182	[1268, 1281]	NA
Week 184	[1282, 1302]	[7x -13, 7x+14] for $8 \leq x \leq 252$
Week 188	[1303, 1330]	[7x -13, 7x+14] for $8 \leq x \leq 252$
Week x	[7x -13, 7x+14] for $188 \leq x \leq 332$	[7x -13, 7x+14] for $8 \leq x \leq 252$
...
Week 256	[7x -13, 7x+14] for $188 \leq x \leq 332$	[1779, 1799]
Week 260	[7x -13, 7x+14] for $188 \leq x \leq 332$	≥ 1800
...
Week 336	[2339, 2359]	NA

CONFIDENTIAL

The information contained herein may not be used, disclosed, or published without the written consent of Biogen MA Inc.

Analysis visit	Analysis visit window ¹	
	For subjects who received the first dose of aducanumab in the placebo-controlled period	For subjects who received the first dose of aducanumab in the LTE period
Week 338	≥ 2360	NA
1. Visit windows are derived based on the first dose of aducanumab. 2. The end day of the placebo-controlled period is the last day before the first infusion in LTE for subjects who enter LTE, or the last day in study for subjects who do not enter LTE. 3. The start day of the LTE period is the day of first dose in the LTE period.		

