2 STUDY DESIGN

2.1 Study Overview

Study 221AD302 (EMERGE) is a multicenter, randomized, double-blind, placebo-controlled, parallel-group study in subjects with early AD, including mild cognitive impairment (MCI) due to AD and a subset of mild AD, followed by an optional dose-blinded long-term extension (LTE) period of up to 5 years. Approximately 1605 subjects will be enrolled across approximately 150 centers globally. The primary study objective is to evaluate the efficacy of monthly doses of aducanumab on the CDR-SB relative to placebo. Secondary objectives include assessment of the effect of monthly doses of aducanumab on clinical progression as compared to placebo. The safety of monthly doses of aducanumab will also be evaluated. The objectives of LTE are to evaluate the long-term safety and tolerability profile of aducanumab in subjects with early AD, and to evaluate the long-term efficacy of aducanumab treatment as measured by clinical, radiological, and health-outcomes assessments.

Subjects will be randomized in a 1:1:1 ratio to 1 of the 3 treatment groups: aducanumab high dose, aducanumab low dose and placebo, with stratification based upon their apolipoprotein E4 (ApoE ϵ 4) carrier status (carrier/non-carrier) and site. During the placebo-controlled period, subjects will receive infusions of aducanumab or placebo approximately every 4 weeks for approximately 18 months (a total of 20 doses). Dose levels may be different in the same treatment group based upon subjects' ApoE ϵ 4 carrier status, and specifically, ApoE ϵ 4 carriers will receive placebo, aducanumab 3 mg/kg, or aducanumab 10 mg/kg whereas ApoE ϵ 4 non-carriers will receive placebo, aducanumab 6 mg/kg, or aducanumab 10 mg/kg. Aducanumab will be titrated for up to 6 doses prior to reaching the target dose as shown in

CONFIDENTIAL

The information contained herein may not be used, disclosed, or published without the written consent of Biogen MA Inc.

Table 1 and Figure 1. Note: As of Protocol Version 4, 10 mg/kg is the target dose for all ApoE ε4 carriers in the high-dose group. ApoE ε4 carriers who were randomized to the high dose group when the target dose was 6 mg/kg (under protocol versions prior to Version 4) must have received 2 or more doses at 6 mg/kg prior to being titrated up to 10 mg/kg.

Table 1: Dosing Scheme for Aducanumab by Treatment Group and ApoE ε4 Carrier Status: Placebo-controlled Period

Dose (every 4 weeks)		1	2	3	4	5	6	7 to 20

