At the end of the double-blind, placebo-controlled treatment period, subjects who meet the extension entry criteria may enter a long-term safety and efficacy extension period, with all subjects receiving aducanumab approximately every 4 weeks (up to a total of 65 doses over 5 years). The treatment group for the LTE period will be assigned at the same time as the randomization for the placebo-controlled period, regardless of whether a subject entering the LTE period or not. Subjects who are assigned to the placebo group during the placebo-controlled period will be assigned to 1 of 2 active treatment groups in a 1:1 ratio (aducanumab low dose: aducanumab high dose) and randomization will be stratified by their ApoE ε4 carrier status; for those who enter the LTE period, aducanumab will be titrated for up to 6 doses prior to reaching the target dose following the same schedule described for the placebo-controlled period. Subjects who are assigned to either aducanumab low dose or aducanumab high dose group in the placebo-controlled period will continue in the same treatment group for the LTE period; those who enter the LTE period will maintain the dosing scheme outlined in the protocol at the time of transition from the placebo-controlled period to the LTE period (e.g. subjects who are on stable dosing in the placebo-controlled period will continue on the same dose, subjects who are on a titration regimen during the transition will continue to titrate into the LTE period, and ApoE ε4 carrier subjects who are enrolled in the LTE and randomized to the high-dose group prior to implementation of version 4 of the protocol will be allowed to titrate to 10 mg/kg). Aducanumab will be titrated for up to 6 doses prior to reaching the target dose for the late start subjects as shown in Table 2 and Figure 1.

CONFIDENTIAL

The information contained herein may not be used, disclosed, or published without the written consent of Biogen MA Inc.

Table 2: Dosing Scheme for Aducanumab by Treatment Group and ApoE ε4 Carrier Status: Long-Term Extension Period

Doses (every 4 weeks)		1	2	3	4	5	6	7- EOS	
LTE Treatment Group	LTE Treatment Group Stratified by ApoE Status ¹	Dose (mg/kg)							
Early Start High Dose	Early Start High Dose – ApoE ε4 (+)	10							
	Early Start High Dose – ApoE ε4 (-)	10							
Early Start Low Dose	Early Start Low Dose – ApoE ε4 (+)	3							
	Early Start Low Dose – ApoE ε4 (-)	6							
Late Start High Dose	Late Start High Dose – ApoE ε4 (+)	1	1	3	3	6	6	10	

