	Late Start High Dose – ApoE ε4 (-)	1	1	3	3	6	6	10	
Late Start Low Dose	Late Start Low Dose – ApoE ε4 (+)	1	1	3					
	Late Start Low Dose – ApoE ε4 (-)	1	1	3	3	3	3	6	

¹ ApoE ε4 status recorded in the Interactive Voice/Web Response System (IXRS).

Individual dose adjustments may be implemented in subjects who develop amyloid related imaging abnormalities (ARIA). See Protocol Section 7.2.1.

The total duration of study participation for each subject only participating in the placebo-controlled period of the study will be up to approximately 102 weeks, including a series of screening visits within 8 weeks before administration of the first dose, a 76-week placebo-controlled treatment period, and a safety follow-up (FU) period of approximately 18 weeks after the final dose. The total duration of study participation for each subject participating in the placebo-controlled period and the LTE period will vary and be up to approximately 362 weeks, including a series of Screening visits within 8 weeks before administration of the first dose, a 76-week placebo-controlled treatment period, a 4-week FU period, a 256-week aducanumab dose-blind treatment period, and a safety FU period of approximately 18 weeks after the final dose.

[figure not shown]
Investigators, study site staff (except for the designated unblinded pharmacist/technician), and study subjects will be blinded to the subjects' randomized treatment assignment for the placebo-controlled period. During the LTE period, investigators and subjects will remain blinded to the treatment assignment in the placebo-controlled period and the aducanumab dose for the LTE period.

CONFIDENTIAL

The information contained herein may not be used, disclosed, or published without the written consent of Biogen MA Inc.

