3.1.2 Analyses period

Depending on the purpose, different analyses will be conducted on the following study periods:

1. LTE period. Only data in the LTE period will be included in these analyses. For example, incidence table of adverse events in the LTE period.
2. Placebo-controlled and LTE period. All the data in the placebo-controlled and LTE periods will be included in these analyses. For example, mean plot of actual laboratory values in the placebo-controlled and LTE period.
3. Placebo-controlled and LTE active treatment period. Active treatment period is defined as the study period(s) that a subject is assigned to aducanumab. For early start subjects – subjects who are assigned to aducanumab in both placebo-controlled and LTE period, all the data (placebo-controlled and LTE periods) will be included in the analyses. For late start subjects – subjects who are assigned to aducanumab in the LTE period, only data in the LTE period will be included. For example, incidence table of adverse events in the placebo-controlled and LTE active treatment period.

Subjects to be included in a certain output is determined by both the analysis population and the analysis period. For example, the incidence table of adverse events in the LTE period will include subjects in the safety population for the LTE period, i.e., all randomized subjects who received at least one dose of study treatment in the LTE period. The incidence table of adverse events in the placebo-controlled and LTE active treatment period will include subjects in the safety population for the active treatment period, i.e., all randomized subjects who received at least one dose of study treatment in the active treatment period. In this SAP we do not separately define the analysis population in each analysis period.

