Due to the different length of placebo-controlled and LTE active treatment period in early start versus late start subjects, both incidence tables and follow-up adjusted incidence rate tables will be used for AE analyses in this period. The entire follow-up time is from the first dose in active treatment period (first dose in placebo-controlled period for early start subjects and first dose in LTE period for late start subjects) until the last day in the study.

	Statistical Analysis Plan Long-Term Extension Period	Final V1.0
---	---	-------------------

The following incidence and follow-up adjusted incidence rate tables will be provided for the placebo-controlled and LTE active treatment period (presented both by LTE treatment group and by LTE treatment group stratified by ApoE status, unless otherwise specified):

1. AEs by system organ class and preferred term sorted by decreasing frequency
2. AEs by system organ class, high level group term and preferred term (by LTE treatment group)
3. AEs by preferred term
4. Severe AEs by system organ class and preferred term (by LTE treatment group)
5. Severe AEs by preferred term
6. Related AEs by system organ class and preferred term
7. SAEs by system organ class and preferred term
8. SAEs by preferred term
9. Related SAEs by system organ class and preferred term

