3.5.3.2 Incidence and summary of ARIA

Incidence of ARIA-E, ARIA-H, ARIA-E and ARIA-H (not necessarily concurrent), concurrent ARIA-E and ARIA-H, ARIA-E or ARIA-H, isolated ARIA-H (only ARIA-H, no ARIA-E), ARIA-H microhemorrhage, ARIA-H macrohemorrhage and ARIA-H superficial siderosis in the LTE period and in the placebo-controlled and LTE active treatment period will be summarized based on both AE eCRF and MRI data. If there is any discrepancy in incidence between the two data sources, a listing of the subjects and ARIA events with discrepancy will be provided. In addition, the incidence table based on AE eCRF source will also be done by LTE treatment group (analysis display A in Appendix 4.1).

Number of subjects with each type of ARIA, maximum severity and worst symptomatic status of the type of ARIA being analyzed in the LTE period and in the placebo-controlled and LTE active treatment period will be summarized based on AE eCRF. For subjects with symptomatic ARIA, the maximum severity of symptoms will also be summarized.

Summary of concurrent ARIA-E and ARIA-H will be provided including the following information for the LTE period and for the placebo-controlled and LTE active treatment period: number of subjects with concurrent ARIA-E and ARIA-H (and further broken down to each type of ARIA-H), the severity of ARIA-E based on MRI, the symptomatic status of ARIA-E, the severity of symptoms based on AE eCRF. For subjects with recurrent ARIA-E

CONFIDENTIAL

The information contained herein may not be used, disclosed, or published without the written consent of Biogen MA Inc.

events, if there is an event concurrent with ARIA-H, it will be used for the summary, and the first concurrent event will be used if there are more than one event concurrent with ARIA-H.

An incidence table of AEs considered by the investigator to be related to ARIA by system organ class and preferred term for subjects with symptomatic ARIA in the placebo-controlled and LTE active treatment period will be provided, as well as a listing of these AEs. Similarly, an incidence table of AEs related to ARIA for subjects with symptomatic ARIA and severe symptoms will be provided, as well as a listing of these AEs.

Listings of AE records for each type of ARIA events and listings of MRI assessments for subjects with each type of ARIA events will be provided.

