3.5.4.2 Qualitative analyses

For qualitative analyses, all values will be included (not just the “analyzed record” within each visit window in the quantitative analyses).

Shift analyses

Laboratory data will be summarized using shift tables where appropriate for the placebo-controlled and LTE active treatment period. Each subject's hematology, blood chemistry and urinalysis numeric values will be flagged as "low", "normal", or "high" relative to the normal ranges of the central laboratory or as "unknown" if no result is available. Each subject's urinalysis categorical values will be flagged as "positive" or "negative", or "unknown" if no value is available.

Shifts from baseline to high/low status will be presented for hematology, blood chemistry and urinalysis numeric parameters, and shifts from baseline to abnormal (positive) will be presented for urinalysis categorical parameters. Shift to low includes normal to low, high to low, and unknown to low; Shift to high includes normal to high, low to high, and unknown to high. Subjects need to have at least one post-baseline evaluation and a baseline value not low or high or positive (including missing) in order to be included in the analysis.

For early start subjects, the placebo-controlled baseline will be used and shifts that occurred in either placebo-controlled or LTE period will be included. For late start subjects, the LTE baseline will be used and shifts that occurred in the LTE period based on LTE baseline will be included.

Grade analyses

Worst post-baseline grade will be summarized for each laboratory parameter in both exclusive way and cumulative way for the placebo-controlled and LTE active treatment period. Subjects need to have at least one post-baseline evaluation in the active treatment period in order to be included in the analysis. Common Toxicity Criteria for Adverse Events v4.0.3 (CTCAE) published on 2010-06-14 will be used for grade determination. Grade determination is based solely on laboratory values not taking AEs into account.

Potentially Clinically Significant laboratory abnormalities analyses

Please refer to the placebo-controlled SAP for the parameters and criteria for potentially clinically significant laboratory abnormalities analyses.

The number of subjects with potentially clinically significant laboratory abnormalities post-baseline will be summarized for the placebo-controlled and LTE active treatment period.

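### LTE SAP 3.5.4.2 and 3.5.5 to 3.5.7 set ever-abnormal percentages for early and late start side by side over active periods that can differ by 80 weeks, without the time adjustment given to AEs

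*SAP*

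**What the plan says.** All sections are in the LTE SAP unless stated.

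- **Period (3.1.2).** The active treatment period is the time a subject is assigned to aducanumab. Early-start subjects contribute both study periods. For subjects first assigned to aducanumab "in the LTE period, only data in the LTE period will be included". The safety population for this period is everyone dosed in it, so early-start subjects who never enter the extension are counted.
- **Length (2.1).** Participation in both periods includes "a 76-week placebo-controlled treatment period, a 4-week FU period, a 256-week aducanumab dose-blind treatment period". The placebo-controlled period has 20 infusions; the extension has "up to a total of 65 doses over 5" years.
- **Vital signs (3.5.7).** "The incidence and percentage of clinically relevant outliers determined by each criterion will be summarized in the placebo-controlled and LTE active treatment period".
- **Laboratory (3.5.4.2).** For the same period, "Worst post-baseline grade will be summarized for each laboratory parameter in both exclusive way and cumulative way". Shifts, potentially clinically significant values and hepatotoxicity are handled the same way, and all values count, not one per visit window.
- **C-SSRS and ECG (3.5.5, 3.5.6).** Also ever-event counts over the active treatment period.
- **AEs (3.5.2.2).** "Due to the different length of placebo-controlled and LTE active treatment period in early start versus late start subjects", follow-up adjusted rates are added to the incidence tables.
- **ARIA.** ARIA-E has a follow-up adjusted rate (3.5.3.3), an exposure-adjusted rate (3.5.3.4) and a Kaplan-Meier plot (3.5.3.5). Section 3.5.3.2 plans incidence of "ARIA-H microhemorrhage, ARIA-H macrohemorrhage and ARIA-H superficial siderosis in the LTE period and in the placebo-controlled and LTE active treatment period".

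Display A in Appendix 4.1 puts late-start and early-start columns next to each other.

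**The concern.** The chance of being abnormal at least once rises with the number of assessments and the time observed. A subject with 20 more infusion visits has more chances to cross a vital-sign threshold even if the drug carries the same risk at every visit. The SAP accepts this reasoning for AEs, gives it as its reason for adding rates, and then does not apply it to the laboratory, C-SSRS, ECG and vital-sign tables. Those sections plan no rate, no common time window and no extension-only version.

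A reader comparing the columns could take an artefact of observation time for an effect of longer treatment. Because the artefact changes with the length of extension follow-up, the same tables could also tell different stories at different data cuts.

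**Working it through.** **1. Reproduce the stated durations.** 8 + 76 + 4 + 256 + 18 = 362 weeks, as stated. (20 − 1) × 4 = 76 weeks and (65 − 1) × 4 = 256 weeks, also as stated.

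**2. The gap, for a subject who enters and completes the extension.**
- Early start: 76 + 4 + 256 = 336 weeks and 20 + 65 = 85 infusions.
- Late start: 256 weeks and 65 infusions.
- Difference: 80 weeks and 20 infusions.

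For vital signs, taken at about every infusion visit, the excess is about 20 visits. For laboratory data, Table 5 has 11 post-baseline windows for early start and 7 for late start, an excess of 4.

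**3. Ever-abnormal proportion at equal risk, extension entrants only.** Formula: 1 − (1 − p)^n. The documents give no per-visit risk, so p is assumed and visits are taken as independent.

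| Data | Visits, early v late | p | Early | Late |
|---|---|---|---|---|
| Vital signs, 1 extension year | 34 v 14 | 1% | 29% | 13% |
| | | 2% | 50% | 25% |
| Vital signs, full length | 85 v 65 | 1% | 57% | 48% |
| | | 2% | 82% | 73% |
| Laboratory windows, full length | 11 v 7 | 1% | 10.5% | 6.8% |
| | | 5% | 43.1% | 30.2% |

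For p from 0.1% to 2%, the early:late ratio is 2.51 to 2.11 with 13 extension doses (33 v 13 visits) and 1.29 to 1.12 with all 65.

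**4. Add early-start subjects who never enter the extension.** With constant hazard h per year, L extension weeks, a fraction q not entering and their mean active follow-up m weeks:
- Late = 1 − exp(−hL/52).
- Early = (1 − q)[1 − exp(−h(L + 80)/52)] + q[1 − exp(−hm/52)].

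Assume h = 0.10, q = 30% (borrowed from the planning drop-out rate in section 3 of the placebo-controlled SAP) and m = 40. Non-entrants then contribute 0.3 × 7.4% = 2.2 percentage points.
- L = 52: early 0.7 × 22.4% + 2.2% = 17.9%; late 9.5%; ratio 1.88.
- L = 104: ratio 1.27.
- L = 156: ratio 1.07.
- L = 256: early 0.7 × 47.6% + 2.2% = 35.5%; late 38.9%; ratio 0.91.

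Across q of 20% to 40%, m of 20 to 94 weeks and h of 0.02 to 0.30, the ratio is 1.40 to 2.36 at 52 extension weeks and 0.72 to 1.11 at 256.

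**5. Which adjustment works.** Section 3.5.1 defines two rates. The follow-up adjusted rate divides by all follow-up, including time after the event. At h = 0.10 for extension entrants it gives, early against late:
- One extension year: 0.224/2.54 = 0.088 v 0.095/1 = 0.095.
- Full length: 0.476/6.46 = 0.074 v 0.389/4.92 = 0.079.

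Both ratios are about 0.93 rather than 1. The exposure-adjusted rate stops the clock at the first event, so under a constant hazard it estimates that hazard in both groups and the ratio is 1.

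**6. ARIA-H.** The placebo-controlled SAP (4.5.3.1 and Table 6) has ARIA events entered as AEs with their own preferred terms. ARIA-H therefore falls within the follow-up adjusted AE tables of LTE SAP 3.5.2.2. Microhemorrhage and macrohemorrhage share one preferred term, so those tables cannot separate them.

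**The case against.** These tables are descriptive and carry no test. The LTE SAP names early-versus-late comparisons only for efficacy (3.3.1) and amyloid PET (3.4.4), and the safety displays also show low against high dose, which the period mismatch does not affect. Changes from baseline in laboratory and vital-sign values are summarised by visit on time since first aducanumab dose, and listings flag the study period of each record. All of this stands and limits the consequence. It does not make the adjacent early and late percentages comparable.

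The visit-based figures rest on independence. Many vital-sign criteria are changes from the subject's own baseline, so repeat abnormalities probably cluster within subjects and the growth with visits would be smaller. That also stands: the figures illustrate, they do not predict.

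Three stronger readings are tempting, and the documents do not support them:
- **That early start will always look worse.** The early-start denominator includes subjects who never enter the extension, with short follow-up, while late start holds only entrants. The difference can vanish or reverse at full length.
- **That ARIA-H has no time adjustment.** It has an extension-only incidence table and follow-up adjusted AE rates by preferred term. Only type-specific rates in the dedicated ARIA outputs are absent.
- **That every table has 20 extra assessments.** That fits vital signs. Laboratory data have 4 extra scheduled windows, and the ECG, C-SSRS and MRI schedules are left to the protocol.

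**Conclusion.** The point holds for the laboratory, C-SSRS, ECG and vital-sign ever-event tables. Their raw percentages are not comparable between early and late start, and the SAP leaves out an adjustment that it makes for AEs for the same reason. At equal risk the early-start percentage is inflated at short extension follow-up: by a factor of 1.40 to 2.36 at 52 extension weeks across the scenarios that allow for non-entry. At 256 weeks the factor is 0.72 to 1.11, so neither a persistent excess nor its direction can be claimed there. These sizes rest on assumed risks, constant over time, and on assumed non-entry and follow-up. The 80-week gap itself comes directly from the stated durations.

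For ARIA-H only a small gap remains: no exposure-adjusted rate or Kaplan-Meier output by type.

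**What to change.** 1. In 3.5.4.2, 3.5.5, 3.5.6 and 3.5.7, add one of the following for each ever-event table: (a) the exposure-adjusted incidence rate of 3.5.1, from first active dose to first abnormality or, if none, to the last relevant assessment, as 3.5.3.4 does with the last MRI; or (b) Kaplan-Meier estimates at common times since first active dose. Option (b) is preferable if risk is thought to change with time on drug, because (a) equalises the groups only under a constant hazard.
2. Keep the whole-period counts, labelled as descriptive and not for comparing early with late start.
3. In 3.5.3.4 and 3.5.3.5, add rows for ARIA-H microhemorrhage, macrohemorrhage and superficial siderosis.

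A plain cut at 80 weeks from first active dose would not be enough. At one extension year it leaves about 20 visits against 14, or 18% v 13% at 1% per visit. The shared Week 72 laboratory window also differs by column in Table 5: days 421 to 525 for early start, 421 to 588 for late start.

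The cost is a few extra descriptive outputs and some SAP wording. Both methods are already planned for ARIA-E, and the laboratory and vital-sign windows already run from first aducanumab dose.
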